13.2. Secondary outcome variables

13.2.1. Safety outcomes:

- Changes in vital signs: During psilocybin session, monitoring of heart rate, blood pressure, respiratory frequency and oxygen saturation.
- Adverse events (AEs) and serious adverse events (SAEs): Longitudinal follow-up and analysis of the relationship with psilocybin-assisted psychotherapy (see section 7).
- Suicidal risk: suicidal ideations or plans will be assessed via the C-SSRS at each visit (see section 5.1)
- **Delirium:** signs of delirium will be assessed through the CAM (see section 5.1)

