5.1.2 Treatment regimen

Version Date: April 18, 2023

Visit V1: baseline assessment + preparation session #1 (patient's home or remote)

V1 includes baseline assessment and a first preparation session with the study therapists (see section below for details about the therapy dyads).

Baseline assessment consists in patient-reported questionnaires that patients will complete on paper either on their own prior to V1 or with the help of a study staff member. Baseline assessment includes the following measurements (see details in section 5.1.5): the Functional Assessment of Chronic Illness therapy – Palliative Care (FACIT-Pal); the PROMIS pain interference scale (if pain presented); the Hospital Anxiety and Depression Scale (HADS A and D); the PROMIS social isolation scale; the Life Attitude Profile – revised, Death acceptance subscale (LAP-R, DA); the FACIT-spirituality; the Schedule of Attitudes Toward Hastened Death (SAHD). Consenting caregivers will complete the CarGOQoL and HADS at V1. In addition, the study psychiatrist will complete the C-SSRS and the CAM.

Following baseline assessments, the lead therapist (LT) and the co-therapist (CT) will conduct the first preparation session. The main objectives of the preparation sessions are to educate

patients and families on psilocybin-assisted therapy, to build rapport between them and the study therapists, and to identify intentions for the psilocybin session as well as personal themes and struggles that might impact the psilocybin experience.

V1 and V2 will be conducted within about a week to a month prior to the psilocybin session.

The duration of V1 will be up to 90 min (30 min assessment + 60 min preparation).

Visit V2: preparatory session #2 (patient's home or remote)

The second preparatory session (V2) will take place at home or remotely. Patients and therapists will conduct V2 assessments as indicated on the schedule of assessment (see 5.1.6) and continue to set expectations for treatment, discuss set and setting and build the therapeutic alliance.

The duration of V2 will be up to 75 min (15 min assessment + 60 min preparation).

Visit V3: psilocybin session (hospice facility) – day 0

The psilocybin session will take place in an individual room at the Care Dimensions Hospice House and will last 8 h (30 min assessment + 7h30 hour psychotherapeutic support).

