Participants will arrive at 8 am and complete the following assessments at V3, prior to receiving the medication: DS-II and HADS A and D. In addition, the lead therapist will complete the C-SSRS and the CAM.

The participant will take the study drug capsule (psilocybin 25 mg) under the therapy team supervision as soon as possible – typically between 9 and 9:30 am. No dose modifications will be necessary.

Blood pressure and heart rate will be measured at the following time-points after psilocybin administration: 30, 60, 120, 180, 240, 300, and 360 min.

During the psilocybin session, facilitators' role will be to monitor, assist and support patients while they are experiencing the effect of the medicine. The monitoring will focus on vital signs and distress level. The assistance and support, whether it's physical or emotional will follow patients' needs in a non-directive way. At the onset of the study agent effect, therapists will invite participants to lie down on the bed, put on eyeshades and put on headphones that will play a pre-selected play-list throughout the session. Therapists will encourage participants to focus inward and stay open to and present with whatever their inner experience is.

Psilocybin effect on perception and consciousness lasts 4 to 6 hours in most individuals. When the participant appears to have returned to his/her baseline psychological and physiological state, and he or she expresses a readiness to begin the discharge process, they will complete the Mystical Experience Questionnaire (MEQ-30) and the Challenging Experience Questionnaire (CEQ), and the Lead Therapist and co-investigator will determine if participant is safe and ready to be discharged home. Patients who are unable to be discharged home for medical or psychiatric

reasons will have the possibility to stay overnight at the hospice house for medical supervision. If for any reason the patient cannot stay at the hospice house and their situation requires medical supervision, arrangements would be made by the study team to admit them to a hospital.

Visit V4: Integration session #1 (patient's home or remote) – Day 1 (up to day 3)

The integration session 1 will occur the day after the psilocybin session (allowable window 3 days) and start with medical and psychological assessment as indicated on the schedule of assessments.

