Functional Assessment of Chronic Illness Therapy-Spiritual Well-Being 12 (Baseline [V1], V5, V6a,b...)

The FACIT-sp-12 scale is a measure of spiritual well-being validated for use in cancer and widely used in palliative care research. ^{47,48} The FACIT-sp-12 has subscales that measure faith, meaning and peace, which are broadly consistent with conceptual models of spiritual well-being. ⁵⁵

Estimated time for administration: 2 minutes

Mystical Experience Questionnaire (V3 [end of session] or V4)

The MEQ-30⁵⁶ is a self-report questionnaire that evaluates discrete mystical experiences induced by serotoninergic psychedelics and is sensitive to detecting psilocybin-induced mystical experiences.⁷ In addition to a MEQ total score, the questionnaire generates four empirically derived factors: mystical; positive mood; transcendence of time and space; and ineffability. *Estimated time for administration: 10 minutes*

Challenging Experience Questionnaire (V3 [end of session] or V4)

The CEQ is a validated instrument with 26 items rated on a 5-item Likert scale, characterizing psychologically difficult aspects of experiences occasioned by psilocybin, according to seven factors: grief, fear, death, insanity, isolation, physical distress, and paranoia.⁵⁷ *Estimated time for administration: 5 minutes*

Schedule of Attitudes toward Hastened Death (Baseline [V1], V6a)

The SAHD is a reliable and valid measure of desire for death among terminally ill patients. It includes 20 items that subjects rate as true or false. 58,59

Estimated time for administration: 5 minutes

Columbia-Suicide Severity Rating Scale (Baseline V0, [V1], V2, V3, V4, V5)

The C-SSRS will be used to assess suicide potential or tendency as a study entry criterion and monitored throughout the study.

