The C-SSRS is a semi-structured interview designed to assess the severity and intensity of suicidal ideation, suicidal behavior, and non-suicidal self-injurious behavior over a specified time period. The measurement of suicidal ideation is based on five "yes" or "no" questions with accompanying descriptions arranged in order of increasing severity. If the patient answers "yes" to either questions 1 or 2, the intensity of ideation is assessed in five additional questions related to frequency, duration, controllability, deterrents, and reasons for the most severe suicidal ideation. Suicidal behavior is assessed by asking questions categorizing behaviors into actual, aborted, and interrupted attempts; preparatory behavior; and non-suicidal self-injurious behavior. If any item(s) on the C-SSRS are answered "yes", the primary investigator or physician investigator must review the patient's responses in order to (a) at screening and Baseline determine the patient's study eligibility and potential need for referral to a mental health professional, and (b) during the study evaluate the patient's need for appropriate medical management such as a referral to a mental health professional.

A significant suicide risk is defined by suicidal ideation with intend and a plan as endorsed on item 5 on the C-SSRS within the past month at V0 or since previous visit later during the study. This must be reported as an AE or SAE as appropriate and followed up accordingly. Additionally, if a patient responds "yes" to any of the suicidal ideation questions 1 through 3, the investigator should apply clinical judgment to determine the need for reporting this as an AE or SAE and the need for any appropriate referral.

The C-SSRS will be collected at every visit.

Estimated time for administration: 3 minutes

Confusion Assessment Method (Baseline V0, [V1], V2, V3, V4, V5)

The CAM will be used to assess delirium as a study entry criterion and monitored throughout the study.

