11. STUDY CALENDAR

11. ST UD		DAK							
	Full screenning + enrollment	Preparation session 1	Preparation session 2	Psilocybin session	Integration session 1 (Day 1)	Integration session 2 (Day 7)	F/U (HOME)	EDC Timepoints	
Visit	VO	V1	V2	V3	V4	V5	V6a,b,,f		
Timing	At least 48h prior to the psilocybin session (V3)	Baseline ≤3 weeks prior to Day 0	≤7 days prior to Day 0	Day 0	Day 1	Week 1 Day 7	Week 3 Monthly after Week 3 Until Week 24 or death	N/A	
Allowable Window					Up to Day 3	Up to Day 14	±14 Day		
Location	Home/Remote	Home/Remote	Home/Remote	Hospice	Home/Remote	Home/Remote	Home/Remote		
Psilocybin				25 mg				V3	
Psychotherapy - min (staff)		60 (LT-CT)	60 (LT-CT)	7h30 (LT-CT)	60 (LT-CT)	60 (LT-CT)		Psychotherapy notes should be captured after V1, V2, V3 V4 and V5	
Assessment - min (staff)	60 (LT-RA)	30 (LT-RA)	15 (LT-RA)	30 (LT-RA)	15 (LT-RA)	30 (LT-RA)	30 (RA)	N/A	
			Clinic	al Assessments and Proced	lures				
Informed consent patient	√							N/A	
Informed consent cargiver	√							N/A	
Demographics	√							V0	
Medical and psychiatric history	√							V0	
Inclusion/exclusion criteria	√							V0	
PPS	√	✓	√	√	√	√	√	During all visits	
САМ	√	✓	√	√	√	√		V0, V1, V2, V3, V4, V5	
C-SSRS (1)	√	✓	√	✓	✓	√		V0, V1, V2, V3, V4, V5	
Vital signs (2)	√			✓				V0, V3	
Physical examination (2)	√			√				V3	
Prior/concomitant medication	√	✓	√	√	√	√		N/A	
Medication taper (if applicable)	√	√	√					NA	
AE/SAEs		✓	√	√	√	√	√	During all visits	
Session recording		✓	√	√	√	✓		NA	
Qualitative interview patient						✓		NA	
Qualitative interview caregiver (3)						√		NA	
Qualitative interview hospice staff							✓	NA	
nospice stan			Particip	pant Completed Assessmen	nts (8)				
DS-II	✓	✓	√	✓	√	√	√	During all visits	
HADS A and D (4)		√	✓	√	√	✓	√	During all visits	
FACIT-Pal 14		✓				√	√	V1, V5, V6a,b,,f	
PIS (6)		✓				√	√	V1, V5, V6a,b,,f	
LAP-R		✓				√	√(7)	V1, V6a	
SIS		√				√	✓	V1, V5, V6a,b,,f	
FACIT-sp		√				✓	✓	V1, V5, V6a,b,,f	
MEQ-30 (5)				✓				V3 or V4	
CEQ (5)				√				V3 or V4	
SAHD		√				✓	√(7)	V1, V6a	
RRPQ						√		V4 or V5	
CarGOQoL (3)		✓				√	√	V1, V5, V6a,b,,f	
Abbreviations IT: Lead Ther		1 1 1 1 1 1 1 1 1 1 1 1 1 1 1 1 1 1 1 1			1	10 : 510/70 !		L	

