Abbreviations. LT: Lead Therapist; CT: Co-Therapist; PA. Research Assistant; DS-H: Demoralization Scale-II; HADS A and D: Hospital Anxiety and Depression Scale Anxiety and Depression; FACIT-Pal 14: Functional Assessment of Chronic Illness Therapy Palliative Care 14; PIS: Pain Interference Scale; LAP-R: Life Attitude Profile – revised, Death acceptance subscale; SIS: Social Isolation Scale; FACIT-Sp 12: Functional Assessment of Chronic Illness Therapy-Spiritual Well-Being 12; MEQ-30: Mystical Experience Questionnaire; CSQ: Challenging Experience Questionnaire; SAMD: Schedule of Attitude toward Hastened Death; C-SSRS: Columbia-Suicide Severity Rating Scale; CAM: Confusion Assessment Method; PPS: Palliative Performance Scale; RRPQ-R: Reactions to Research Participation Questionnaire Revised; CarGOQoL: CareGiver Oncology Quality of Life questionnaire.

(1) The "Last month" version will be administered at Screening (V1) and the "Since Last Visit" version will be administered at all other visits.

⁽a) Lares lever only
(d) These assessments will also be completed by the participant's cargiver at V1, V5 and V6a,...f
(e) Only if the patient indicates pain at a given assessment period.
(f) Only at V6a
(g) We anticipate that given their terminal condition, participants might not be able to complete these questionnaires or may only be able to complete part of them. To reduce administrative burden, we will not report those missing questionnaires as protocol violations.

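### The text promises the C-SSRS at every visit, but the calendar stops it at V5, so suicidal risk has no C-SSRS data at V6a-f and no item-specific review trigger takes its place

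*Combined protocol and SAP*

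**What the plan says.** Section 13.2.1 lists suicidal risk among four safety outcomes and states that "suicidal ideations or plans will be assessed via the C-SSRS at each visit", with a pointer to Section 5.1. Within 5.1.5, the instrument entry is headed "Columbia-Suicide Severity Rating Scale (Baseline V0, [V1], V2, V3, V4, V5", yet its text ends with "The C-SSRS will be collected at every visit".

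In the Section 11 calendar, the C-SSRS row is ticked through V5, the V6 cell is empty, and the EDC column reads "V0, V1, V2, V3, V4, V5". Note 1 to the calendar assigns the last-month form to screening and says that the since-last-visit "version will be administered at all other visits".

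Section 5.1.4 treats V6a and the later monthly contacts as visits. They run to Week 24 or death. The calendar staffs research assessment there by the research assistant alone; V0 to V5 list the lead therapist as well.

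After any positive C-SSRS answer, Section 5.1.5 says "the primary investigator or physician investigator must review" the responses. There is no comparable sentence for the DS-II or the SAHD, which Section 13.2.2 lists as efficacy outcomes.

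**The concern.** Exploring safety is a secondary objective, and the C-SSRS is the only instrument named for the suicidal-risk outcome. Sites and data managers work from the calendar and the EDC build. The likely result is therefore that C-SSRS collection ends at V5 while the outcome definition still claims every visit, and any later report on suicidal risk would describe a shorter period than its definition implies.

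The V6 forms still put related questions to patients. DS-II item 14, on preferring not to be alive, is asked at every V6 visit. SAHD items 4, 5 and 18, on seeking help to die, considering steps to end life and planning to do so, are asked at V6a. With no C-SSRS at those visits, the one rule that obliges an investigator to look at such answers does not operate.

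**Working it through.** The plan gives no figure to reproduce. The check is a side-by-side reading, followed by simple counts.

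**1. Schedule statements**

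| Place | C-SSRS timing |
|---|---|
| 13.2.1, safety outcomes | Each visit (defers to 5.1) |
| 5.1.5, instrument text | Every visit |
| 5.1.5, instrument heading | V0-V5 |
| 11, calendar row and EDC column | V0-V5 |
| 11, calendar note 1 | All other visits; mainly assigns the form version, so ambiguous |

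The empty V6 cell is not a loss in text extraction, because the EDC column and the 5.1.5 heading independently stop at V5. The CAM shows the same mismatch: its 5.1.5 heading and calendar row give V0-V5, and its text says every visit.

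**2. What is left uncovered on the calendar**

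- Visits: V6a-f are 6 visits, and 0 of 6 have a C-SSRS.
- Days: the last C-SSRS is at Day 7 (window to Day 14). Follow-up to Week 24 is 24 x 7 = 168 days. Uncovered: 168 - 14 = 154 to 168 - 7 = 161 days for a patient who lives that long.

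**3. Related items still collected at V6**

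- DS-II item 14 (Appendix A4): V6a-f. The printed recall period is two weeks, so with visits about 28 days apart it spans 14/28 = 50% of the interval. A since-last-visit C-SSRS would span all of it.
- SAHD items 4, 5 and 18 (Appendix A14): V6a only.
- Investigator-review rule in 5.1.5: C-SSRS answers only.

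**4. Scale (illustrative only)**

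Assumptions: exponential survival from dosing, no other dropout, and visits at Days 21, 49, 77, 105, 133 and 161. S(t) = 0.5^(t/median). The 43-day median comes from 13.3.1, which gives it as a lower bound for PPS of 50% and above; 90 days is an assumed alternative.

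- 43 days: S = 0.713, 0.454, 0.289, 0.184, 0.117, 0.075; sum 1.832 visits per treated patient. For 10 to 15 treated patients: 18.3 to 27.5 V6 visits.
- 90 days: sum 3.183, giving 31.8 to 47.7 V6 visits.
- C-SSRS time at 3 minutes each (5.1.5): 10 x 1.832 x 3 = 55 to 15 x 1.832 x 3 = 82 minutes over the whole trial; with 90 days, 95 to 143 minutes.

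**The case against.** The best defence is that every visit is shorthand for the screening and treatment visits. Section 13.2.1 defers to Section 5.1, where the heading says V0-V5. Note 1 sits on a calendar row ticked only to V5. The CAM wording follows the same pattern. On this view a wording edit is enough. The point has weight: a tally of statements for and against would mislead, and note 1 should not be counted as evidence. But Section 5.1.4 calls V6a and its successors visits, and the sentences in 5.1.5 and 13.2.1 carry no limit, so the conflict stands and needs an edit in one direction or the other.

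A reader might infer that a patient who marks one of these items at V6 has no route at all to an investigator. The documents do not support that. The calendar keeps AE/SAE collection at V6, Section 7 sends potential adverse events to the principal investigator, Section 5.1.2 allows unscheduled visits or calls for safety, and the hospice team continues care after V5. Nor does the staffing entry show that the research assistant works unsupervised. The treatment manual and any working instructions are not among the documents, so a step may exist there.

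What remains is narrower. These general routes depend on someone recognising the answer as a potential event, and the protocol does not say that it is one. The duty in 7.4.2 also ends 30 days after last treatment: Day 30 if counted from dosing, at most Day 14 + 30 = Day 44 if counted from V5, and both precede the nominal V6b at Day 49.

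It is also fair to say that a wish for death can be a settled view in hospice. That argues against automatic adverse events, but not against a clinician looking at the answer.

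**Conclusion.** The concern holds in this form. Two unrestricted promises (5.1.5 text and 13.2.1) conflict with the 5.1.5 heading and with the calendar and its EDC column. On the calendar, the suicidal-risk outcome has no C-SSRS data at any of the 6 V6 visits. Separately, there is no item-specific trigger for DS-II item 14 at V6a-f or SAHD items 4, 5 and 18 at V6a, although general safety channels remain open.

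This rests on the text alone and assumes only that staff follow the calendar. The visit and minute counts depend on the survival assumptions and show scale; they do not estimate how many answers would be missed. No feasibility benchmark, test or analysis population changes. The correction should be made because it affects a stated safety outcome and is cheap.

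**What to change.** **Preferred.** Add the since-last-visit C-SSRS to V6a-f in the 5.1.5 heading, the calendar row and the EDC column, with the existing investigator review applying. Name who gives it. At V1 "the study psychiatrist will complete the C-SSRS and the CAM" and at V3 "the lead therapist will complete the C-SSRS and the CAM", so V6 needs either a trained research assistant or a clinician call.

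**Add to 5.1.5.** The person collecting the form passes to the investigator, at that visit, any of these post-dose answers:

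- true on SAHD item 4, 5 or 18;
- DS-II item 14 scored 2;
- DS-II item 14 higher than at V1;
- DS-II item 14 scored 1 or more when the V1 score is missing.

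The investigator applies clinical judgment, and the flag is not an automatic adverse event. Flagging every score of 2 matters because a patient already at the maximum at V1 could never be picked up by a rule based on worsening alone.

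**Alternative.** If the sponsor wants the C-SSRS at V0-V5 only, correct the 5.1.5 text and 13.2.1 to say so, and flag any non-zero DS-II item 14 score at V6, since no C-SSRS would then back up the rule. The CAM wording should be reconciled in the same amendment.

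**Cost.** About 3 minutes per V6 visit, training or a clinician call, and a few investigator reviews, some of which will reflect settled views about dying.

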13.2.2. Efficacy outcomes

Global quality of life: FACIT-Pal 14

Physical domain: PIS

• Psychological domain: HADS A and D; LAP-R; CEQ

• Social domain: SIS

• Spiritual domain: FACIT-sp; DS- II; SAHD; MEQ-30

• Caregiver quality of life and psychological distress: CarGOQoL; HADS A and D

13.3. Sample size and statistical plan

13.3.1. Sample size justification

Patients with a PPS score of 50% and above have a median survival of 43 days or greater.⁷³ We anticipate that we will need to treat at least 10 patients for feasibility data to be relevant. To account for patients who are unable to complete the intervention because of clinical decline, we plan to recruit 15 patients.

Assuming that treatment and week 1 assessment will be completed on 10-15 patients, the 90% exact binomial confidence intervals for the feasibility rate will be between (30.3%-85.0%) – for 10 patients - and (36.0%-81.0%) – for 15 patients.

Assuming that between 6 (out of 10) and 9 (out of 15) patients will be able to assess the acceptability, the 90% exact binomial confidence intervals for the acceptability rate will be between (41.8% - 99.1%) – for 10 treated patients, out of which 60% deem the procedure "feasible" - and (57.1% - 99.4%) – for 15 treated patients, out of which 60% deem the procedure "feasible".

We will use the treatment effect size calculated for this study to inform the sample size of the upcoming corresponding confirmatory trial.

Accrual targets are as follow:

Accrual Targets								
Ethnic Category	Sex/Gender							
Etimic Category	Females		Males		Total			
Hispanic or Latino	2	+	1	=	3			
Not Hispanic or Latino	6	+	6	=	12			
Ethnic Category: Total of all subjects	8 (A1)	+	7 (B1)	=	15 (C1)			
Racial Category								
American Indian or Alaskan Native	0	+	0	=	0			
Asian	1	+	1	=	2			
Black or African American	2	+	1	=	2			
Native Hawaiian or other Pacific Islander	0	+	0	=	0			
White	5	+	5	=	10			

Racial Category: Total of all subjects	8 (A2)	+ 7 (B2)	= 15 (C2)
	(A1 = A2)	(B1 = B2)	(C1 = C2)

13.3.2. Safety analysis

The Safety Population will consist of all enrolled participants who receive study treatment. This population will be used for all summaries of participant accountability, demographic and baseline data, and safety information, including AE incidence.

The Full Analysis Set (FAS) will consist of all participants who receive the dose of psilocybin and will be used for all summaries of efficacy.

The Per Protocol (PP) population will consist of all participants in the FAS who do not have a major protocol deviation which is defined as a deviation which may significantly affect efficacy for that participant. Major protocol deviations will be reviewed and determined prior to database lock.

13.3.3. Efficacy analysis

Since this is a single treatment open-label study, no statistical testing will be performed. We will use descriptive statistics and thematic coding to analyze quantitative and qualitative data respectively, and joint display for the integration of the two.

Qualitative analysis will deploy thematically coding of interview transcripts using content analysis, an inductive and deductive approach. At least two investigators with experience in qualitative analysis will independently code the first four interviews. They will compare their coding, refine common theme, identify new themes, and iteratively refine the codebook. Discrepancies will be resolved through discussion with other investigators until consensus is reached. We will use Dedoose qualitative analysis software to support content analysis.

The FAS and PP populations will be used for each secondary efficacy endpoint (change in respective scores from baseline (V1) to Week 1 (V5), Week 3 (V6a) and subsequent monthly visits until death or Week 24), if the two sets are not identical. For each of the secondary endpoints, measuring change from Baseline, a repeated measures analysis will be performed. Comparisons with baseline will be performed at the 0.05 testing level. Secondary endpoints that are dichotomous variables (for example, proportion of participants who are responders, remitters and sustained remitters) will be summarized as frequencies. Scores for all efficacy endpoints will be summarized over time using descriptive statistics for all visits during the observation period.

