1.3 Secondary Objectives

To explore the safety of psilocybin-assisted therapy in this population and its preliminary efficacy on demoralization and other patient-reported and family caregiver-reported outcomes.

Hypotheses:

No serious adverse-event related to the intervention will occur and week 1 outcomes assessment will show improvement in demoralization.

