The interviews with hospice staff will be conducted in-person or remotely (over the phone or a DFCI Zoom account), last **about 40 min** and be audio-recorded. Audio recording will start only after participant's information and verbal consent, according to the interview script attached. Recording will be transcribed verbatim using a HIPAA compliant service. All recordings and transcripts will be stored in secure, restricted-access locations. Recordings and transcripts will be tied to a unique study ID number, and the only documents linking the study ID to identifiable information are in restricted access files stored securely in restricted access folders. Potential patient's health information will be de-identified, and all audio recordings will be destroyed when analyses are complete.

5.1.5 Instruments measuring study outcomes:

Demographic questionnaire (V0)

Version Date: April 18, 2023

Variables of interest will be obtained via self-report and include: age, ethnicity, race, marital status, education, and occupational status.

Medical Record Review (V0, V5, V6a,b...)

A member of the study team will record clinical data, including diagnosis, disease stage, and treatments. Comorbidities or current medical history will also be extracted from medical records.

Demoralization Scale-II (Baseline [V1], V5, V6a,b...)

The DS-II measures of the experience of disheartenment and helplessness and is well validated in terminally ill patients. As It's a 3-point response, self-report scale comprising 16 items and 2 subscales (meaning and purpose, and distress and coping ability). The presence of baseline moderate-to-severe demoralization, as measure by a DS-II score ≥ 8 , is necessary for inclusion in this study. For V5 assessment, we will ask subjects how they felt over the past week instead of over the past two weeks as originally framed in the instrument.

Estimated time for administration: 3 minutes

Hospital Anxiety and Depression Scale (Baseline [V1], V5, V6a,b...)

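### Section 13.3.3 rules out statistical testing and then requires comparisons with baseline at the 0.05 level, and no scale or visit is named as the source of the effect size for the confirmatory trial

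*Combined protocol and SAP*

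**What the plan says.** Section 13.3.3 (Efficacy analysis) opens with "Since this is a single treatment open-label study, no statistical testing will be performed" and assigns descriptive statistics to the quantitative data. Its last paragraph says "For each of the secondary endpoints, measuring change from Baseline, a repeated measures analysis will be performed", followed by "Comparisons with baseline will be performed at the 0.05 testing level". The comparisons run from V1 to V5, V6a and the monthly visits, in the full analysis set and, where it differs, the per-protocol set. Sidedness, a multiplicity rule and the status of the p-values are not given.

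Section 1.3 states one efficacy hypothesis, that "week 1 outcomes assessment will show improvement in demoralization". Section 5.1.5 gives the matching instrument and visits: "Demoralization Scale-II (Baseline [V1], V5, V6a,b" and onward. Section 13.2.2 places the scale in the spiritual domain, unranked: "FACIT-sp; DS- II; SAHD; MEQ-30".

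Section 13.3.1 says: "We will use the treatment effect size calculated for this study to inform the sample size of the upcoming corresponding confirmatory trial". It names no scale, visit, analysis set or estimator.

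**The concern.** Two competent analysts could each claim to follow section 13.3.3 and produce different reports, one with no p-values and one with many unadjusted ones. In an uncontrolled pilot of at most 15 patients, an unlabelled p-value below 0.05 is easily over-read.

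The effect size matters more in practice, because it feeds the next trial. If scale and visit are settled after the data are seen, the choice can drift towards the most favourable result. The confirmatory trial would then be planned on an effect that is too large on average.

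**Working it through.** **1. The two statements side by side.** The opening of section 13.3.3 excludes testing, and the sentence after it limits quantitative work to description. The closing paragraph sets a significance level for comparisons with baseline. In a single-arm study those comparisons are the only quantitative tests the section could mean, so the exclusion and the requirement cover the same analyses. No other section reconciles them.

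**2. The plan's own figures.** Section 13.3.1 gives 90% exact binomial intervals. Clopper-Pearson limits reproduce them within 0.1 percentage point:

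| Count | Recomputed | Plan |
|---|---|---|
| 6/10 | 30.4 to 85.0% | 30.3 to 85.0% |
| 9/15 | 36.0 to 80.9% | 36.0 to 81.0% |
| 5/6 | 41.8 to 99.1% | 41.8 to 99.1% |
| 8/9 | 57.1 to 99.4% | 57.1 to 99.4% |

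These concern feasibility and acceptability only. No figure in the plan supports the 0.05-level comparisons.

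**3. Counting change endpoints (sections 13.2.2 and 5.1.5).**
- Patient: FACIT-Pal 14, PIS, HADS-A, HADS-D, SIS, FACIT-sp, DS-II, LAP-R, SAHD = 9.
- Caregiver: CarGOQoL, HADS-A, HADS-D = 3.
- Total 9 + 3 = 12. MEQ-30 and CEQ describe the dosing session and have no baseline.

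**4. False positives under no change, one overall test per endpoint.** Two-sided testing is an assumption.
- Expected number: 12 × 0.05 = 0.6.
- At least one, independent: 1 − 0.95^12 = 0.460.
- At least one, equally correlated normal test statistics (400,000 simulated draws): 0.399, 0.319 and 0.233 at correlations of 0.3, 0.5 and 0.7.
- Patient endpoints only: 9 × 0.05 = 0.45 expected; 1 − 0.95^9 = 0.370 if independent.

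**5. Why larger counts are not used.** Testing every endpoint at every visit would give up to 72 tests: 10 at V5, 12 at V6a and 10 at each of five later visits. That needs survivors to test. Section 13.3.1 says patients with a PPS of 50% and above "have a median survival of 43 days or greater". Assuming exponential survival from dosing at that floor, with all 15 dosed:
- Week 11: 15 × 2^(−77/43) = 4.3 alive.
- Week 23: 15 × 2^(−161/43) = 1.1 alive.

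With an assumed median of 86 or 120 days, 8.1 or 9.6 would be alive at Week 11. The number of usable late comparisons is therefore unknown.

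**6. Choosing the effect size afterwards.** Section 5.1.5 schedules seven patient change scales at Week 1 (the nine above without LAP-R and SAHD). Take no true change, equal correlation between scales, and each mean change divided by its own SD of change. The average of the largest favourable value over 100,000 simulated trials is:

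| Correlation | n = 15 | n = 10 |
|---|---|---|
| 0.3 | 0.317 SD | 0.408 SD |
| 0.5 | 0.270 SD | 0.347 SD |
| 0.7 | 0.209 SD | 0.272 SD |

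For comparison, the 95% confidence half-width for one mean change is t(0.975, n−1)/√n, which is 0.55 SD at n = 15 and 0.72 SD at n = 10. The study calendar also ticks LAP-R and SAHD at V5, although its data-capture column lists only V1 and V6a. With nine scales the n = 15 range would be 0.35 to 0.23 SD.

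**The case against.** The best defence is that the opening sentence means only that no between-treatment tests are done, since there is one treatment. The text does not say that, and its next sentence restricts quantitative analysis to description. The contradiction stands.

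Other parts of the defence do hold:

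- A reader might infer that section 13 drops the section 1.3 hypothesis. It does not. Sections 13.2.2 and 13.3.3 together cover DS-II change from V1 to V5. Demoralization is also the target condition (sections 1.1 and 1.3) and an entry criterion (section 3.1.5), so DS-II is the natural source for the next trial's effect size. What is missing is an explicit statement, and free choice among seven scales is a worst case.
- A reader might infer that familywise control is required. Efficacy is a secondary, exploratory objective, so a clear label is enough.
- A reader might infer that naming DS-II in advance yields an unbiased effect. It removes selection among scales only. Patients enter on DS-II of 8 or more, so regression to the mean can produce apparent improvement. V5 also asks about one week, whereas the original instrument asks about two. The baseline visit is unclear too: section 5.1.2's list of V1 measures omits DS-II, while section 5.1.5 and the calendar include it.

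**Conclusion.** Section 13.3.3 contradicts itself in current text and should be corrected. The source of the effect size in section 13.3.1 should be named. The primary feasibility and acceptability conclusions do not depend on either point.

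The sizes are illustrative. For 12 endpoints tested once each, 0.6 false positives are expected, and the chance of at least one is 46% if independent or 40% to 23% if correlated. Post-hoc choice of the best Week 1 scale would add, at worst, 0.32 to 0.21 SD (n = 15) or 0.41 to 0.27 SD (n = 10). The false-positive figures assume two-sided tests, which the plan does not state. Both sets of ranges assume equal correlations of 0.3 to 0.7 and no true change. The documents do not support a firm claim of dozens of tests, because late visits may have too few survivors.

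**What to change.** Preferred: keep the no-testing sentence and delete "Comparisons with baseline will be performed at the 0.05 testing level". State that the repeated measures analysis estimates mean change, with 95% confidence intervals that are descriptive and unadjusted for multiplicity.

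If the sponsor prefers to test: delete the no-testing sentence instead, state sidedness, and name DS-II change from V1 to V5 as the one principal test. Then either run no other tests or label the others nominal.

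In both cases:
- Name DS-II change from V1 to V5 in the full analysis set, with its SD and 95% interval, as the section 1.3 contrast and the source of the section 13.3.1 effect size.
- State that baseline is the V1 score, not the V0 screening score used for entry, and bring section 5.1.2's V1 list into line with section 5.1.5 and the calendar.
- Report as limitations regression to the mean from entry on DS-II and the shorter recall period at V5.

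Cost: a protocol wording amendment, mainly to section 13. No patients, visits or measurements are added. The sponsor gives up, or relabels, p-values on exploratory endpoints.
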